2. BACKGROUND AND RATIONALE

Chronic edema of the lower limbs (i.e., chronic peripheral edema) is a common condition. Peripheral edema can cause pain, heaviness, weakness, discomfort, negative body image and limit mobility and flexibility. Limitations to mobility can reinforce a sedentary lifestyle, which exacerbates peripheral edema, leading to a vicious cycle of disease. Furthermore, when peripheral edema is untreated, it causes increased risk of infection and ulcers.² Nineteen percent of older US adults surveyed in the 2016 wave of the Health and Retirement Study³ reported persistent lower limb swelling (manuscript in preparation). It affects many individuals, including those with obesity, older age, sedentary lifestyles, history of deep venous thrombosis, and occupations that require long periods of standing.^{4,5} Considering the high rates of obesity in the US, peripheral edema is a large and likely growing public health challenge.⁴ No cure for peripheral edema exists. Some types of edema are responsive to diuretics,⁴ but these medications cause frequent urination. Dietary restrictions, such as limiting salt intake, can reduce edema as well. However, lifestyle changes are challenging to implement and sustain, especially for lower income patients for which easy access to whole foods is lower. Compression stockings are generally accepted as the standard of care treatment to contain swelling associated with edema. However, many patients find compression stockings to be uncomfortable or even painful, embarrassing, hot in the summer, and itchy. Taken together, improved treatments for chronic peripheral edema are highly warranted.

Peripheral edema is caused by increased interstitial fluid volume. The interstitial fluid volume is controlled by a delicate balance between hydrostatic pressures in the plasma and interstitial space, which are controlled by the venous and lymphatic systems. Underlying health conditions affect fluid (i.e., water and dissolved solutes) flow out of the arterial end of the capillaries into the interstitial space. The majority of this fluid is reabsorbed back into the venous end of the capillaries. The remaining net increase in interstitial fluid is removed via the

Page 1 of 26

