- (2) General Impression of change in Edema. The subject's impression of change in edema symptoms will be measured using a single question (i.e., General Impression of Edema form) that utilizes a 1 7 scale adapted from the patient global impression of change (PGIC). ¹⁸ The scale uses the anchors "very much improved", "much improved", "minimally improved", "not changed", "minimally worse", "much worse", or "very much worse" [1 = very much improved, 7 = very much worse]. The PGIC is commonly used in chronic pain trials to assess subjects' experiences of the change from the beginning of a treatment or clinical trial. ¹⁹
- (3) **General Impression of change in Activity**. Impression of change in ability to be active will be measured using a single question (i.e., **General Impression of Activity** form) that utilizes a 1 7 scale adapted from the PGIC.¹⁸ The measure uses the anchors "very much improved", "much improved", "minimally improved", "not changed", "minimally worse", "much worse", or "very much worse" [1 = very much improved, 7 = very much worse]. The PGIC is commonly used in chronic pain trials to assess patients' experiences of the change from the beginning of a treatment or clinical trial.¹⁹

Subjects will record the medications taken for edema each day on the **Edema Symptom Daily Diary**. The coordinator will ask the subject if they take certain medications known to affect swelling and if they take any medications to treat their peripheral edema. The coordinator will customize the medication diary portion of the **Edema Symptom Daily Diary** to include these medications only.

A qualitative interview will be performed to explore how subjects prefer to rate the symptoms associated with peripheral edema, what additional symptoms were not asked about, and what aspects of the subject's life are affected by their edema. The responses will be recorded on the Treatment **period Endpoint-Qualitative** forms.

Page 6 of 26

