5. INCLUSION AND EXCLUSION CRITERIA

Inclusion criteria (subjects must...)

- 1. Have had lower extremity edema for at least 3 months.
- 2. Currently have edema of at least 2+ (i.e., 3-4mm depression rebounds within a few seconds, but not immediately) on the pitting scale. ²¹ Pitting will have been assessed by a Clinician, the clinician Co-I within 6 weeks of the screening visit or at the screening visit by the research staff.
- 3. Willing to not start or change the dosages of any medications that could affect edema for 2 weeks prior to enrollment, and throughout the duration of the study.
- 4. Not currently using diuretics to control their edema.
- 5. Not currently using and willing to not start using occupational therapy, physical therapy, or lymphatic massage for edema (at home or by PT) 2 weeks prior to and throughout the duration of the study.
- 6. Not currently using compression stockings or Velcro or bandage wraps at least 2 weeks prior to enrollment in the study or based on shared decision making of the potential subjects' clinician or the clinician co-investigator are receiving sufficiently little benefit from these therapies to warrant stopping their use for the duration of the study.
- 7. Have access to a smart phone or device with an Apple or Android operating system with iOS 10 or later, or Android 6 or later. iOS and Android devices must have Bluetooth Low Energy (LE, also called Bluetooth Smart) compatibility. The smart phone or device must have the ability to access the TENS device's Quell App and, the ability to connect to the cellular data or Wi-Fi on a daily basis during the trial.
- 8. Have an active and accessible email.
- 9. Be willing and able to regularly check the email provided throughout the study.
- 10. Be able to read English (i.e., is literate, can speak English, and is not blind) because patient-reported outcomes and consent form are only available in English.
- 11. Be at least 18 years of age.
- 12. Be able to provide informed consent.

Exclusion criteria (subjects must not...)

- 1. Be currently using a TENS device for any reason.
- 2. Have an acute and symptomatic lower extremity DVT (i.e., the diagnosis of DVT is less than 3 months prior to study enrollment).
- 3. Have had a stroke in the past 3 months
- 4. Have lower extremity wounds or ulcers.
- 5. Have a cardiac pace maker or defibrillator.
- 6. Have epilepsy.
- 7. Have a leg that is too small or too large for the TENS device to fit securely.

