9. RISKS TO SUBJECTS

Potential risks from stopping use of compression stockings or wraps: If subjects choose to forgo use of compression stockings or wraps to start the trial, there is a risk that their edema could worsen during the study. We have minimized this risk by only enrolling subjects who are not experiencing a significant of benefit from these therapies (i.e., entry criteria: "based on shared decision making of the potential subjects' clinician or the clinician co-investigator [the potential subject is] receiving sufficiently little benefit from these therapies to warrant stopping their use for the duration of the study"). Subjects will be asked to call the study staff if they feel as though their swelling or symptoms are worsening and they will decide together with the clinician Co-I if they should stop using the TENS device and resume using compression stockings or wraps.

Potential risk of not trying currently available treatment options: For some people, the following treatments can be tried for peripheral edema, (1) compression stockings, (2) Velcro wraps, (3) manual lymphatic drainage, (4) short stretch bandage wrapping, (5) pneumatic pumps, (6) kinesiotape, (7) acupuncture, and (8) cupping. For potential subjects who have not been offered these treatments in the past, choosing to join the study and forgoing these treatments could lead to a worse outcome than if they tried one of these alternative treatments. The potential subjects will be informed of these alternative treatment options and given the opportunity to consult their primary care physician or the clinician Co-I regarding whether they should consider the alternative treatments prior to starting the study.

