16. DATA ANALYSIS PLAN

Missing Data

All efforts will be made to prevent missing data. Due to the exploratory nature of the study, missing data will not be accommodated statistically.

Sample Size Estimation

We plan to recruit 52 people for this study because it is what we think is feasible given our resources and should provide sufficient information to determine whether there is a reasonable potential efficacy signal to move forward to a randomized clinical trial.

Aim1. Feasibility Analyses

(1) Descriptive statistics will be used to summarize all feasibility outcomes. (2) Common themes in subject-reported reasons for low adherence will be summarized in the qualitative data.

Aim 2. Preliminary Efficacy

- (1) Primary preliminary efficacy: Preliminary efficacy for the water volume displacement outcome and the Edema Symptom Daily Diary will be assessed using Wilcoxon sign-ranked test comparing the outcomes from Baseline and Treatment Endpoint.
- (2) Secondary preliminary efficacy: Similar analyses to those in the primary preliminary efficacy aim will be used for the secondary efficacy outcomes.

Due to the exploratory nature of the study, no adjustments will be made for multiplicity.

Exploratory Analyses

- 1) Similar analyses to those in the primary preliminary efficacy aim will be used to assess changes between Baseline and Treatment Period Endpoint for the continuous exploratory efficacy outcomes.
- 2) The percentage of subjects whose monofilament threshold improves between Baseline and Double-blind Endpoint will be compared using a Fisher's exact test.
- 3) Trajectories of changes in activity (measured via the Fitbit) and changes in swelling (measured via NRS swelling and symptoms ratings) will be visually inspected and compared to investigate whether increased activity precedes and therefore may contribute to decreased swelling.
- 4) Qualitative analysis techniques will be used to analyze the cognitive interview data to improve self-report measurements for peripheral edema.

Page 24 of 26

5) We will explore the data for patterns to see if people with different causes of edema seem to benefit from the treatment more frequently than others. These qualitative analyses will be used to inform future entry criteria.

REFERENCES

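### Subjects who stop TENS and resume compression mid-study have no rule in the Baseline-versus-Endpoint test, and recording of the switch is not assured

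*Combined protocol and SAP*

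**What the plan says.** Inclusion criterion 6 (Section 5) admits people not using compression. It also admits current users judged to be "receiving sufficiently little benefit from these therapies to warrant stopping their use for the duration of the study". Section 9, under the risks of stopping compression, foresees that some will get worse. They are asked to call the study staff, and "they will decide together with the clinician Co-I if they should stop using the TENS device and resume using compression stockings or wraps".

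Section 13 does not name resumed compression as a reason for withdrawal. It lets subjects decline any activity and stay in the study, and it allows, but does not require, withdrawal of someone who cannot complete study activities. After withdrawal, only data collected up to that point are used.

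In Section 16, preliminary efficacy on the two primary efficacy outcomes, water displacement and the daily diary, "will be assessed using Wilcoxon sign-ranked test comparing the outcomes from Baseline and Treatment Endpoint". The plan adds that "missing data will not be accommodated statistically". It defines no analysis set and no sensitivity analysis for subjects who stop TENS or resume compression.

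On recording, Section 4 has the coordinator tailor the medication part of the diary "to include these medications only". No form in Table 3 is described as recording stocking or wrap use.

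**The concern.** The trial has one arm, so whatever change the test finds is read as the effect of TENS. Section 9 sets out in advance a route by which subjects doing badly on TENS leave it for another treatment before the endpoint. Section 2 describes that treatment in these words: "Compression stockings are generally accepted as the standard of care treatment to contain swelling associated with edema". A Visit 3 value taken after the switch exists and looks complete, but it reflects compression.

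Section 16 says that the results should show whether there is enough signal to justify a randomised trial. A signal that comes partly from compression, or from the loss of worsening subjects, would mislead that decision. Compression use that is not collected during the study cannot be recovered reliably afterwards.

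**Working it through.** **Step 1: follow one switcher through the plan.**
- *Stays and attends Visit 3.* Nothing in Section 16 sets the subject apart. The Visit 3 volume and later diary entries enter the signed-rank test as TENS outcomes.
- *Is withdrawn.* There is no Visit 3 volume, missing values are not handled, and the pair drops out of the volume test. The subject removed is one who was worsening.

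**Step 2: is the switch recorded?**
- The diary's treatment item covers medications only.
- The adverse event form (Section 15) has fields for action taken and for change in device use, so it can capture a switch if the worsening is handled as an adverse event. Table 5 does not mark grade 1 and 2 events judged unrelated or unlikely as recorded. Worsening after giving up compression could plausibly be judged unrelated to the device.
- The Quell App shows that TENS stopped. It does not show that compression resumed.

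Capture is therefore possible but not assured.

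**Step 3: is there a plan figure to reproduce?** There is none for power. The 52 is a feasibility number; the only arithmetic near it is recruitment yield, 150 × 1/3 = 50. No alpha, SD, effect size, switching rate or compression effect is given.

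**Step 4: illustrate the size.** Assumptions: n = 52; TENS has no effect; changes from Baseline are N(0,1), positive meaning more swelling; the k worst-changing subjects switch; compression lowers their endpoint by b SD. The test is the signed-rank statistic W (sum of ranks of improved subjects), with

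Z = (W − n(n+1)/4) / √(n(n+1)(2n+1)/24).

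For n = 52 the mean is 52 × 53/4 = 689 and the SD is √(52 × 53 × 105/24) = √12,057.5 = 109.8. A significant improvement is Z > 1.96, nominally 2.5%. When switchers are dropped, n becomes 52 − k.

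| Handling of switchers | k = 3 (3/52 = 5.8%) | k = 5 (9.6%) | k = 8 (15.4%) |
|---|---|---|---|
| Analysed as observed, b = 0.5 SD | 3.5% | 4.8% | 7.6% |
| Analysed as observed, b = 1 SD | 5% | 10% | 20% |
| Dropped from the test | 12% | 24% | 47% |
| Ranked as worst change | 1.8% or less | 1.8% or less | 1.8% or less |

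With no switchers the simulated rate is 2.5%.

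**Step 5: relax perfect selection.** Suppose instead that switchers are chosen on a mid-study status that correlates 0.5 with the endpoint change. The as-observed rates at 1 SD hardly move (about 6%, 10% and 20%). The dropped rates fall to about 6%, 9% and 15%, so that row of the table leans most on the selection assumption.

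**The case against.** Four objections deserve an answer.

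*The switch is visible to the team.* A reader might infer that no form records the switch and that the analyst could never identify these subjects. The documents do not support that. A switch by the Section 9 route involves the study staff and the clinician co-investigator, the adverse event form has relevant fields, and the app shows TENS stopping. What stands is that recording is not assured and that no dated compression item is described.

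*The documents do not say that switchers stay in.* That is correct; their inclusion is inferred from silence, and discretionary withdrawal is available. But withdrawal does not rescue the test, as the dropped row shows.

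*Compression may do little for these people, and they may still end worse.* A reader might infer that compression turns their worsening into improvement, with a large effect. Criterion 6 speaks against that: people who gave up compression to join were judged to gain little from it. A 2 SD benefit, which would give about 14%, 32% and 68%, is implausible here. At 1 SD, the perfectly selected switchers still end on average 0.9, 0.7 and 0.5 SD worse than Baseline for k = 3, 5 and 8. The worsening is reduced, not reversed, and the false-signal rate still rises.

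*The bias could run against TENS.* If 5 switchers are given a fixed net worsening of 1 SD and everyone else is an unselected null sample, the rate falls to 0.4%; with a net improvement of 1 SD it is 8.0%. So the absolute rate need not exceed 2.5%, particularly if giving up compression itself makes people worse. That model does not compare the same subjects with and without compression, however. On that comparison, any compression benefit moves the test toward TENS.

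The stakes are also limited: feasibility is the first aim, efficacy is exploratory, and a randomised trial would follow.

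**Conclusion.** The point holds as a gap in the analysis rule and in data capture. The plan provides for a switch to another treatment and does not say how the switcher's outcome counts. Relative to the same subjects' uncompressed outcome, both default routes push the primary efficacy test toward a false signal.

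The size cannot be fixed from the documents. With 3 to 8 switchers, the illustration runs from 3.5% to 20% for compression benefits of 0.5 to 1 SD, and from 12% to 47% if the worst-changing subjects are dropped (about 6% to 15% if selection is imperfect). These figures rest on assumed switcher numbers, normal changes, a null TENS effect and a two-sided 5% test. It is not established that switching will be common, that it would go unrecorded, or that switchers would end better than Baseline. This is a cheap improvement.

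**What to change.** 1. Add a daily yes/no item on stocking or wrap use to the Edema Symptom Daily Diary, and record on a coordinator form the dates on which TENS stopped and compression resumed.
2. In Section 16, pre-specify that the as-observed analysis is accompanied by one in which switchers, including those withdrawn after a switch, are counted as non-improved, for example by ranking them worst in the signed-rank test. This is one reasonable choice and a conservative one (1.8% or less against a nominal 2.5%).
3. Report the number of switchers.
4. Reconcile Sections 5, 9 and 13 on whether a subject who resumes compression remains in the study. No change to the clinical decision is proposed.

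The cost is one diary line, two dates and a few sentences in the plan. The efficacy result may look slightly less favourable.

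### The plan is inconsistent on which non-drug edema therapies are restricted during the study and describes no form to record them, so one started or resumed after Visit 2 cannot be told apart from a TENS effect

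*Combined protocol and SAP*

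**What the plan says.** **Section 9 (Risks to subjects)** lists eight available treatments: "1) compression stockings, (2) Velcro wraps, (3) manual lymphatic drainage, (4) short stretch bandage wrapping", then "5) pneumatic pumps, (6) kinesiotape, (7) acupuncture, and (8) cupping". It warns people who have not been offered them that "choosing to join the study and forgoing these treatments could lead to a worse outcome than if they tried one of these alternative treatments". The same section foresees that a subject whose swelling worsens may, after discussion with the clinician co-investigator, stop TENS and go back to stockings or wraps.

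**Section 5, inclusion criterion 5** reads "Not currently using and willing to not start using occupational therapy, physical therapy, or lymphatic massage for edema", from 2 weeks before the study to its end. **Criterion 6** has two branches. The first is "Not currently using compression stockings or Velcro or bandage wraps at least 2 weeks prior to enrollment in the study". The second admits current users judged to be "receiving sufficiently little benefit from these therapies to warrant stopping their use for the duration of the study". Criterion 3, on medications, carries a no-start undertaking like the one in criterion 5.

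**Section 7 (Consent process)** asks every potential subject, as a comprehension check, whether stockings may be worn on study. The expected answer is not printed.

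**Section 4 (Study measures)** describes how co-treatment enters the daily diary: "The coordinator will ask the subject if they take certain medications known to affect swelling", and the medication portion is then customized to those drugs alone.

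**Section 16** tests the two primary efficacy outcomes, water displacement and the daily diary, with a signed-rank comparison of Baseline and Treatment Endpoint in a single arm.

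**The concern.** With no control arm, the only protection against crediting another therapy's effect to TENS is to restrict that therapy, or to record it and account for it. The plan does this for edema medications, which are held stable by criterion 3 and logged in the diary. For non-drug therapies the restriction is written differently in three sections, and no record is described.

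A therapy that reduces swelling and begins between Visit 2 and Visit 3 changes the endpoint but not the baseline, which is exactly how a TENS effect would look. Section 16 says the study should show whether the efficacy signal justifies a randomized trial, so a bias towards improvement is a bias towards going ahead. Without a record, the investigators could not show afterwards whether it happened.

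**Working it through.** **Step 1. Compare the lists.**

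| Treatment in Section 9 | Named in Section 5? | No-start wording? |
|---|---|---|
| Compression stockings | Criterion 6 | Not in the first branch; the second covers current users who stop |
| Velcro wraps | Criterion 6 | As above |
| Short-stretch bandage wraps | Criterion 6 | As above |
| Manual lymphatic drainage | Criterion 5, as lymphatic massage | Yes |
| Pneumatic pumps | No | – |
| Kinesiotape | No | – |
| Acupuncture | No | – |
| Cupping | No | – |

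Coverage by name is 4/8 = 50%. Criterion 5 also bars occupational and physical therapy for edema, so it may reach a pump or taping delivered by a therapist. It does not clearly reach a home pump, self-applied tape, or acupuncture or cupping obtained elsewhere.

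**Step 2. Compare the sections on compression.** For someone not using compression, criterion 6 looks only at the 2 weeks before enrollment. The Section 7 question implies a stocking restriction for all subjects but does not mention Velcro or bandage wraps. Section 9 allows for a return to either on worsening. The three sections do not give one rule.

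**Step 3. Look for a record.** The diary collects symptom ratings and edema medications. No form in Table 3 is described as collecting non-drug edema therapy. Phone Call 1 (Section 8) covers new symptoms and adherence. The AE form (Section 15) records action taken to treat an adverse event, so it would catch a therapy only when tied to a recorded event. No analysis rule covers endpoint data from a subject who resumed compression.

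**Step 4. Illustrate the size.** The plan gives no figure to reproduce: 52 rests on feasibility, with no SD, effect, alpha or power.

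- From the plan: n = 52 and the signed-rank test.
- Assumed: complete pairs; true TENS effect zero; volume change normal with SD 75 or 150 mL; two-sided 5% level; k subjects whose co-treatment lowers volume by d = 100 or 150 mL.
- Shift in mean change = −k × d / 52. For k = 5: −5 × 100/52 = −9.6 mL and −5 × 150/52 = −14.4 mL.
- The probability of p < 0.05 in the direction of a decrease was simulated with 100,000 runs per cell (simulation error below 0.2 percentage points).

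| Starters k (share of 52) | SD 75 mL, d = 100 / 150 | SD 150 mL, d = 100 / 150 |
|---|---|---|
| 0 | 2.5% | 2.5% |
| 2 (3.8%) | 4.5% / 5.1% | 3.6% / 4.0% |
| 5 (9.6%) | 10.2% / 13.6% | 5.8% / 8.0% |
| 8 (15.4%) | 20.1% / 30.2% | 9.3% / 14.5% |

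The result depends heavily on all three assumed inputs. With a couple of starters the distortion is slight. It becomes material at roughly 10–15% of subjects with a large co-treatment effect relative to the SD.

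**The case against.** The strongest reply is that Section 9 is a risk disclosure, addressed to people not previously offered these treatments, and never claims to be a list of prohibited therapies. A reader might infer that the plan forbids all eight and then fails to enforce it. The text does not support that. What stands is narrower: the disclosure speaks of forgoing treatments that no criterion asks subjects to forgo.

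A reader might also infer that subjects not using compression are free to start it. That follows only if criterion 6 is read alone. The consent question points the other way for stockings, so the defect is an unclear restriction, not an absent one. For wraps the gap is more open.

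Nor is the diary blind to everything but drugs, because it records swelling and symptoms. The limit applies to its co-treatment portion. The form itself is not reproduced, so its content is inferred from the description.

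A home pump used at a steady level throughout is present at both visits and largely cancels in a paired test, so only new or resumed use matters. The treatment period is only 3 weeks, and nothing in the plan suggests that 5 or 8 of 52 subjects would start something new. The study is described as exploratory, with no significance threshold tied to the decision to proceed. These points limit the size of the problem. They do not supply the missing record.

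**Conclusion.** The concern holds as an inconsistency plus a recording gap. Sections 5, 7 and 9 do not agree on which non-drug edema therapies are restricted, and no described form would show their use. In a single-arm before–after comparison, such a therapy newly started or resumed after Visit 2 is indistinguishable from TENS.

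The size is not established. The illustrative range, from about 4% with 2 starters to about 30% with 8 against 2.5% by chance, rests wholly on assumed uptake, effect and SD, and should not be read as a forecast. The point is worth correcting because it is cheap and because the data could not settle the question afterwards. It does not invalidate the study.

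**What to change.** 1. Reconcile Sections 5, 7 and 9 so that they state one position on which co-treatments are restricted during the study, including how the provision for resuming compression fits. Which therapies to restrict is the investigators' choice.

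2. Whatever list is kept, add one daily line to both the Pre-baseline and the Treatment-period diary: any non-drug edema therapy used today (yes/no, which). Having it in both separates steady use from new use.

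3. Tabulate use by subject and by timing relative to Visit 2.

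4. Add one sensitivity run of the two primary signed-rank tests in which subjects who newly started or resumed such a therapy after Visit 2 are counted as not improved. Do not drop them: some will have worsened and returned to compression, and removing them would favor TENS. Specify the scoring in advance. A change of zero will not serve, because the usual signed-rank procedure discards zeros. A rank on the worsening side does the job and should be labelled a conservative bound.

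The cost is an edit to three sections, one diary line with slightly more burden for subjects, one table and one extra analysis run.
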